101 hypothesize that there is a moderate to strong positive correlation between the specificity of
102 the prompts and the quality of evidence-based health risk communication provided by LLMs.

103 3. Compare the evidence-based quality of responses generated by laypeople with varying levels
104 of informed prompting by comparing the quality of LLM responses based on prompts
105 generated by laypeople who provide varying levels of detail and information. We will assess
106 whether layperson-generated prompts result in more evidence-based responses than low-
107 informed prompts, but less so than moderately informed prompts.

108 RQ3: Are LLM responses generated by laypeople more evidence-based than those from low-
109 informed prompting, but less so than moderately informed prompting? We hypothesize that
110 Layperson-generated prompts produce more evidence-based responses compared to low-
111 informed prompts, but less so than moderately informed prompts that include about 50% of
112 key health decision-making information.

113 4. Evaluate the impact of a minimal boosting intervention on the quality of LLM responses by
114 assessing whether a minimal boosting intervention—where users are encouraged to provide
115 more specific prompts by considering the consequences of their health decisions—can
116 improve the evidence-based quality of LLM responses.

117 RQ4: Does a minimal boosting intervention increase evidence-based responses? We
118 hypothesize that reminding users to consider the consequences of their choices will lead to an
119 increase in evidence-based responses, improving the overall adherence of LLM outputs to
120 guideline-based communication standards.

121 5. Test the digital native hypothesis: RQ5: Without boosting intervention, digital natives (defined
122 as participants under 30 years of age) do not prompt a higher quality of LLM responses than
123 people from the age of 30 years and more.

124 **Trial Design**

125 The study is divided into two phases. Phase 1 uses a content analysis design to evaluate LLM responses
126 to standardized prompts. Phase 2 is a randomized between-subjects experiment with a 1:1 allocation
127 ratio, comparing standard prompting (control group) and enhanced prompting (intervention group).
128 Each group will interact with LLMs under similar conditions, but with differing levels of instruction
129 specificity.

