130 Given that this study is entirely web-based, there are no onsite requirements for integrating the AI
131 intervention into the trial setting. All interactions with the LLMs will occur remotely, facilitated through
132 the SoSci Survey platform, hosted by the University of Potsdam. The integration of the AI systems (Open
133 AI ChatGPT, Google Gemini, and Mistral AI Le Chat) is managed through an API, ensuring seamless
134 communication between the survey platform and the LLMs.

135 For offsite requirements, participants will need access to a digital device (computer, tablet) with a
136 stable internet connection to interact with the LLMs and complete the survey.

137 There is no need for any physical infrastructure or on-premises installations, as the entire intervention
138 process, from user prompts to LLM responses, will be executed in the cloud through secure, encrypted
139 connections.

140 **Methods**

141 This protocol was developed in adherence to the Guidelines for clinical trial protocols for interventions
142 involving artificial intelligence: the SPIRIT-AI extension.¹⁵

143 **Phase 1: Systematic Evaluation of LLM Responses to Predefined Prompts**

144 In the first phase of the study, we will systematically assess the quality of outputs generated by
145 OpenAI's ChatGPT, Google Gemini, and Mistral AI. The LLMs will respond to a set of predefined,
146 standardized English-language prompts related to BC and PC screening. These prompts will encompass
147 a range of typical patient inquiries, such as the risks and benefits of cancer screenings, the
148 interpretation of screening results, and the overall recommendation for undergoing screening. Each
149 LLM will respond to multiple iterations of the same prompts, allowing for an assessment of both
150 consistency and variability in the responses.

151 In total, six (decision preparation elements) times three distinct (in specificity varied) prompts will be
152 repeated 20 times across three LLMs and two screening topics, resulting in 2,160 total responses to be
153 scored. An additional scoring across six prompts (full decision preparation) will be based on nine
154 evaluation criteria of the compliance with context information standards (e.g. declaration of conflict of
155 interest). Each LLM response will be evaluated against predefined quality metrics, by independent
156 human raters using the validated MappInfo tool for the evidence-based quality assessment of digital

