245 responses will be excluded.

246 Phase 2, Participants:

248 The exclusion criteria for selecting the Participants in the study will be the following:

- 249 - Health Professionals: Individuals with professional expertise in healthcare, particularly in
250 cancer screening or health communication, will be excluded to avoid bias and ensure that
251 participants reflect the general lay population.
252 - Previous Experience with LLM Studies: Participants who have taken part in similar studies
253 involving LLMs will be excluded to prevent familiarity with the technology from influencing the
254 results.

255 **Procedure and material**

256 Phase 1:

257 Researchers will prompt LLMs via API and collect the responses.

258 Phase 2:

259 Participants will receive a brief introduction outlining the study's purpose, which involves interacting
260 with one of three LLMs [OpenAI ChatGPT (gpt-3.5-turbo)¹⁷, Google Gemini (1.5-Flash)¹⁸, or Mistral AI
261 Le Chat (mistral-large-2402)]¹⁹, all preset as a "helpful assistant" to obtain health information of either
262 BC or PC screening. Following informed consent, participants will be asked to provide basic
263 demographic details such as gender, age, and education level through a questionnaire interface built
264 with SoSci Survey. They will then be given the choice to receive information about either BC or PC
265 screening. Participants will engage with the chatbot by entering their queries (prompts) through the
266 LLM's API, and the generated responses will be collected alongside the prompts for systematic analysis.
267 At the end of the session, participants will be asked about their frequency of LLM usage, their prior
268 experience with such models, and their perspectives on how an informed decision-making process
269 should ideally be conducted for them, by choosing one from four options.

270 A pre-test with n=20 participants will be conducted to verify the effectiveness of the randomization
271 procedures, ensuring balanced group assignment, the technical functionality of the survey platform
272 and its integration with the LLM APIs. Additionally, the average completion time will be measured and
273 potential issues related to participant burden will be identified. Feedback on user experience will be
274 collected to address any usability concerns. Based on these findings, necessary adjustments will be
275 made at the protocol for the main trial.

276 **Tests and Outcomes**

277 Primary Outcome:

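### RQ3 sets lay-prompted answers on a self-chosen topic against Phase 1 references fixed at half breast and half prostate, and nothing in the stated analysis aligns the topic mix

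*Protocol*

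**What the plan says.** The hypothesis for RQ3 (Protocol, Objective, item 3) is two-sided in structure: "Layperson-generated prompts produce more evidence-based responses compared to low"-informed prompts, while scoring below moderately informed prompts that carry about half of the key decision information.

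Prompts of graded specificity are described only for Phase 1: "In total, six (decision preparation elements) times three distinct (in specificity varied) prompts will be" "repeated 20 times across three LLMs and two screening topics, resulting in 2,160 total responses to be" scored. Every prompt is crossed equally with both topics and all three LLMs.

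For Phase 2 (Procedure and material), participants first give demographic details, and then: "They will then be given the choice to receive information about either BC or PC" screening. No passage balances or caps that choice. The model versions and the helpful-assistant preset are stated in the same Phase 2 paragraph. The Phase 1 procedure is one sentence: "Researchers will prompt LLMs via API and collect the responses".

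The Analysis and Statistical Methods sections list t-tests, ANOVA, and linear regression for prompt specificity. They name no contrast specific to RQ3 and do not mention screening topic.

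**The concern.** The protocol does not say outright where the low-informed and moderately informed reference answers come from, but Phase 1 is the only source it describes. RQ3 is therefore a comparison between two phases. The 1:1 randomisation applies inside Phase 2, between the boosted and unboosted arms, and gives RQ3 no protection.

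The two sides of the contrast are averaged over different populations of questions. The reference means carry equal weight for breast and prostate by design, whereas the lay mean carries whatever mix the participants prefer. If LLMs score better on one topic, the lay mean moves relative to both references for a reason unrelated to how lay people write prompts. At stake is the reading of either RQ3 contrast: a true gap between lay and low-informed prompts could be inflated or hidden, and so could the gap to moderately informed prompts.

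**Working it through.** **Inputs from the protocol.** Six elements, three specificity levels, 20 repeats, three LLMs and two topics (Phase 1 section); 300 recruits (Sample Size); 1:1 allocation (Allocation).

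**Inputs assumed.** p, the share of lay participants choosing the higher-scoring topic, and d, the topic difference in SD units. Neither is in the document. Taking the lay group in RQ3 to be the unboosted control arm is also an assumption; it gives 300 / 2 = 150.

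**Step 1: reproduce the plan's figure.** 6 x 3 x 20 x 3 x 2 = 2,160, as stated. This is 2,160 / 2 = 1,080 per topic, 2,160 / 3 = 720 per specificity level, 720 / 2 = 360 per level and topic, and 360 / 3 = 120 per level, topic and LLM.

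**Step 2: shift in the lay mean.** The reference mean puts weight 0.5 on each topic and the lay mean puts weight p on the higher-scoring one. With no prompt effect, the difference is (p - 0.5) x d:

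- p = 0.5, any d: 0
- p = 0.6, d = 0.3: 0.1 x 0.3 = 0.03 SD
- p = 0.7, d = 0.5: 0.2 x 0.5 = 0.10 SD
- p = 0.8, d = 0.5: 0.3 x 0.5 = 0.15 SD

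**Step 3: effect on one contrast.** Treating all responses as independent, SE = sqrt(1/150 + 1/720) = 0.0898 SD. The three non-zero shifts are 0.33, 1.11 and 1.67 SE. The chance that |Z| exceeds 1.96 is then about 6%, 20% and 39%, against a nominal 5%. At an illustrative Bonferroni level of .01 (critical value 2.576), the same shifts give about 1%, 7% and 18%.

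**Step 4: effect on the ordering.** The low and moderate references share the same balanced mix, so the shift has the same sign against both. If prompts made no difference at all, low and moderate would be equal and lay would land above both or below both, not between them. If low and moderate truly differ by G and lay prompts truly equal low ones, a positive shift smaller than G would place lay between them. So the shift can distort one inequality, but the full ordering needs a real difference between low and moderate.

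**Step 5: price of aligning the mix.** Reweighting the 360 + 360 reference responses at a level to topic shares p and 1 - p gives variance [p² + (1 - p)²] / 360. At p = 0.8 this is 0.68 / 360 = 0.00189, against 1/720 = 0.00139 unweighted. The SE of the contrast becomes sqrt(1/150 + 0.00189) = 0.0925, about 3% above 0.0898. Equal topic weights on both sides would cost more. At p = 0.8 the lay variance is 0.25/120 + 0.25/30 = 0.01042, so the SE is sqrt(0.01042 + 0.00139) = 0.1087, about 21% higher.

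**The case against.** The strongest reply is that the protocol specifies no RQ3 test at all. Regression is among the listed methods, topic and LLM are known for every response, and adjustment for them is the kind of detail a statistical analysis plan, not shown here, may carry. This stands in part: the imbalance can be repaired with data already planned. It does not remove the point. The protocol fixes both the self-chosen topic and the balanced reference, and the methods it names, applied as they stand, would average over unlike mixes.

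Second, the size is conditional. The census-based sex quota may keep the choice near 50:50 (itself an assumption), and the mildest case above is negligible. The 720 responses are 20 repeats in 6 x 3 x 2 = 36 cells; allowing for that clustering raises the SE and lowers the rejection rates. This stands, and the rates should be read as illustrations.

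Third, a reader might infer that the phases run under different model versions or presets. The documents do not support that. The same three LLM families are named for both phases and both use an API. Silence about Phase 1 settings leaves them unspecified; it does not show that they differ.

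Finally, letting people choose their topic suits the aim of studying natural lay enquiries. That is accepted, and the fix leaves the choice in place.

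**Conclusion.** The point holds as a comparability gap in RQ3. The lay-versus-reference contrast is unrandomised and, with the methods as stated, is taken over different topic mixes. It is biased only if the chosen mix departs from 50:50 and the topics also score differently. Under the assumed values the shift is 0.03 to 0.15 SD. One two-sided contrast at .05 would then reject about 6% to 39% of the time with no prompt effect, and less under Bonferroni adjustment or with repeats treated as clustered.

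Two stronger readings should be resisted. The shift cannot by itself produce low below lay below moderate, because it pushes lay the same way against both references. The 6% to 39% are also not error rates for RQ3, which needs two directional statements to hold together. The randomised RQ4 comparison does not use the Phase 1 references and is not touched. This is a cheap improvement to a secondary contrast and leaves the main comparison sound.

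**What to change.** Add one sentence for RQ3. Control-arm lay responses are compared with the low-informed and moderately informed Phase 1 responses within the same LLM and topic. The six cell differences are then averaged with the Phase 2 control-arm cell shares as the single stated weighting. This leaves the lay mean as observed and standardises Phase 1 to the lay mix, so the topic-mix shift is zero by construction. Naming one weighting matters, because equal weights would estimate a different quantity and cost more precision.

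As a secondary clarification, state in the Phase 1 procedure that the responses are generated with the same model identifiers and helpful-assistant preset as Phase 2. This needs settling before Phase 1 runs, since no later analysis could repair a mismatch.

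The cost is two sentences, slightly more analysis work and a minor loss of precision in the reweighted references (about 3% on the SE at p = 0.8, on the independence assumption used above). No new data are needed.
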